

XV. LEGAL AND ETHICAL ASPECTS ADMINISTRATIVE CONSIDERATIONS

XV.1 STUDY SPONSOR

The sponsor of the study is the Fédération Francophone de Cancérologie Digestive (FFCD). The study was registered under the number EudraCT 2014-000050-10.

XV.2 REMINDER OF THE TEXTS IN FORCE

This test will be carried out according to the European Directive 2001/20/EC.

XV.3 PUBLIC LIABILITY INSURANCE

Insurance was taken out by the sponsor on 09/01/2014 under the number 137.681 with SHAM, in accordance with Article L 1121-10 of the Public Health Code (Appendix 12).

XV.4 APPLICATION TO CPP AND ANSM

This protocol received the favorable opinion of the PPC (Committee for the Protection of Persons) EST I on 17/04/2014 (Appendix 13).

This protocol received authorization from the ANSM, Agence Nationale de Sécurité du Médicament et des Produits de Santé on 17/06/2014 (Appendix 14).

XV.5 COLLECTION OF THE PATIENT'S CONSENT

The investigator undertakes to collect, after information, the patient's clinical and biological consent in writing (information sheet and consent form in appendices 1 and 16). A copy of these consents must be kept by the investigator for 15 years. The originals must be given to the patient.

In accordance with the recommendations of the Cancer Plan (Measure 4.3.), these documents were submitted for review, advice and guidance to the Patients' Committee for Clinical Research (PCCR) of the National League Against Cancer.

XV.6 INFORMATION TO HOSPITAL MANAGEMENT AND RESEARCH AGREEMENT

Prior to the implementation of the study, the hospital management will be informed by the Sponsor of the investigator's interest in participating in this trial.

A no-cost research agreement will be established between the investigating center administrator and the sponsor.

XV.7 DATA ARCHIVING

The files will remain confidential and can only be consulted under the responsibility of the doctors in charge of the patients. The sponsor and the health authorities in case of inspection will have direct access to these documents.

At the end of the trial, the observation book will be kept for 15 years by the investigator.

XV.8 IT SUPPORT

In accordance with the text of the law n° 78-17 of January 6, 1978 modified by the law of August 9, 2004, relating to data processing, files and freedoms, the data of the trial will be recorded in a data bank of the Center of Randomization and Management Analysis of the FFCD, with the exception of the elements relating to the identity of the patients.

XV.9 DATA PROCESSING

The FFCD's Center for Randomization Management and Analysis (CRGA) will be responsible for data management and analysis.

XV.10 MONITORING, QUALITY ASSURANCE AND INSPECTIONS BY AUTHORITIES

The investigator agrees in advance that the records of the patients included in the trial may be consulted by a person mandated by the FFCD and/or by the health authorities to carry out an audit. On-site monitoring of records, scheduled after agreement with the investigator, may take place during and after the trial inclusion period.

This protocol will be monitored by the FFCD's mobile ARCs.

The investigator agrees to sign the observation books at the end of each visit.

XVI. PUBLICATION

The current FFCD publication rules will be applied (Appendix 11)

XVII. APPENDICES

---

---

## 2 Abbreviations and definitions

CHCC	Carcinoma	Hepatocellular carcinoma
CHE		Chemoembolization
CP		Main criterion
SEE		Serious adverse event
HCC18		Hepatocellular Carcinoma (Quality of Life module)
MRI		Magnetic resonance imaging
ITT		Intention to treat
NCI-CTC		National Cancer Institute Common Toxicity Criteria
TAP		Thoraco-abdomino-pelvic
CT scan		Tododensitometry
TP		Prothrombin rate
RECIST		Response evaluation criteria in solid tumors

### **3 Introduction**

#### **3.1 Objectives of the trial**

##### **3.1.1 Objective main**

The primary objective of the study is to evaluate the objective response rate (complete and partial response) at 6 months, assessed according to mRECIST criteria in centralized review.

##### **3.1.2 Secondary objectives**

The secondary objectives of this study are to evaluate:

- The 6-month objective response rate (mRECIST) assessed by the investigator
- 6-month objective response rate (EASL)
- Time to treatment failure
- The best response according to mRECIST
- Progression-free survival
- Overall survival
- Treatment tolerance
- Quality of life (QLQ-C30 questionnaires and its HCC18 module specific to HCC)

##### **3.1.3 Translational study**

A translational study is planned as part of this trial:

- biological with blood samples for the determination of circulating VEGF and progastrin
- imaging (cone-beam CT) to correlate chemoembolized tumor and non-tumor volume measurements with VEGF assays

### **4 Experimental design**

#### **4.1 Study diagram**

This is a single-arm, multi-center Phase II trial.

#### **4.2 Treatment arms**

[figure not shown]
There is a single study treatment arm consisting of 1 to 4 sessions of chemoembolization (sessions spaced 6 weeks +/- 1) with idarubicin-loaded microbeads (100-300 µm) (10 mg).

#### **4.3 Randomization and blinding**

The trial is open-label. There is no randomization in this trial.

## 4.4 Chronological sequence

Each patient will follow the chronological sequence described below:

## 4.5 Justification of the number of subjects required

The assumptions used to calculate the number of subjects required are :

- H0: A proportion of patients with an objective response at 6 months of 25% or less is not acceptable.
- H1: A proportion of patients with an objective response at 6 months of more than 25% would demonstrate the efficacy of the treatment. A rate of 40% is hoped for.

Using a 2-stage Fleming design (Fleming, 1982) with a one-sided alpha risk of 5% and power of 90%, it is necessary to include **86 evaluable patients**.

Taking into account a 5% rate of patients lost to follow-up or not evaluable, **91 patients** will be included.

## 4.6 Test steps

### 4.6.1 First stage: interim analysis

An interim analysis was performed in January 2017 after inclusion of 46 patients (44 evaluable for the primary endpoint). At this stage, out of 44 evaluable patients, according to the decision rules, 19 or more patients needed an objective response at 6M to judge the treatment effective.

22 patients met this criterion and the treatment was therefore deemed effective. The trial was therefore stopped for efficacy (rejection of H0).

### 4.6.2 Second stage: final analysis

In view of the results of the interim analysis and the discontinuation of the study for efficacy, the final analysis will be performed with a last news date for each patient after 01/01/2017.

### 4.6.3 Transition between the two stages

Not applicable

## 5 Study population for analysis

### 5.1 Definition of analysis populations

#### 5.1.1 Intention-to-treat (ITT) population

The intention-to-treat population is defined as all patients included in the study, irrespective of eligibility criteria and treatment received.

#### 5.1.2 Population of analysis for primary endpoint (CP)

The analysis population for the primary endpoint is defined as all evaluable patients included in the study, regardless of eligibility criteria. A patient is considered evaluable if he or she has undergone at least one chemoembolization and one post-treatment evaluation.

A patient without any imaging will be considered non-evaluable.

A patient who dies within the first 6 months (whatever the cause) is evaluable and considered a failure for the primary endpoint.

Patients without a 6-month assessment will be reviewed according to the following rules:

- If the patient has a later evaluation (6 months or more) and is not in objective response at that date, he/she will be considered as not having an objective response at 6 months.
- If the patient has a documented objective response at more than 6 months without imaging at 6 months, this patient should be reviewed.

A list of patients excluded from the CP population will be provided, together with the reasons for their exclusion.

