## **6.4 Missing data conventions**

Except in the cases specified, missing data will not be replaced.

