## 6.6 Statistics

**Quantitative variables** will be described using headcount, median, mean, standard deviation of the mean, minimum, maximum and inter-quartile range (Q1-Q3). Quantitative variables can be categorized using their median or a cut-off known from the medical literature.

**Categorical variables** will be described using percentages, and if necessary their bilateral 95% confidence intervals (calculated using the exact method).

Missing values are not taken into account when calculating frequencies and percentages.

The **confidence intervals** provided will be two-sided 95% confidence intervals, except for the main criterion where a one-sided 95% confidence interval will be given.

**Survival data** will be estimated and plotted using the Kaplan-Meier method (Kaplan and Meier, 1958). This will be described by the median and rates calculated at different times. 95% confidence intervals will be provided. Confidence intervals for rates will be constructed from the Greenwood variance calculated using the log-log transformation.

The median follow-up time is calculated using the reverse Kaplan-Meier method (Shemper, 1996).

The treatment hazard ratio will be estimated using a univariate Cox model (Cox, 1984). The hypothesis of proportionality of rates will be tested using the graphical representation and test based on Schöenfeld residuals (Grambsch, 1994); the linearity of the effect of continuous variables on risk will be assessed using the graphical representation of martingale residuals. Confidence intervals for Cox model coefficient estimates will be calculated using Wald's method.

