## 7.3 Evaluation of primary endpoint efficacy

#### Population CP

### 7.3.1 Definition of primary efficacy endpoint

The primary endpoint is the objective response rate 6 months after inclusion. Objective response (complete and partial response) is defined according to mRECIST criteria and based on centralized review (or on the investigator's opinion if review is not possible).

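### SAP 5.1.2 sets no 6-month outcome for a living evaluable patient last imaged before 6 months, and no criterion or default for a patient whose response is documented only later

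*SAP*

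**What the plan says.** **Who is in the population.** SAP 5.1.2 takes all evaluable patients as the population for the primary endpoint: "A patient is considered evaluable if he or she has undergone at least one chemoembolization and one post-treatment evaluation". It does not say when that evaluation must take place. Protocol VII.2 schedules liver imaging 4 to 6 weeks after each session, so one early scan is enough.

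**What happens without a 6-month scan.** SAP 5.1.2 states: "Patients without a 6-month assessment will be reviewed according to the following rules". It fixes or announces the following:
- Death within 6 months, from any cause: failure.
- Imaging at 6 months or later that shows no response: "he/she will be considered as not having an objective response at 6 months".
- Response seen only later: "If the patient has a documented objective response at more than 6 months without imaging at 6 months, this patient should be reviewed".

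**General conventions.** SAP 6.4: "Except in the cases specified, missing data will not be replaced". SAP 6.6: "Missing values are not taken into account when calculating frequencies and percentages".

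**Who assesses.** SAP 7.3.1 defines response by mRECIST, "based on centralized review (or on the investigator's opinion if review is not possible"). Protocol X assigns central reading to a panel of independent radiologists. Protocol VII.2 makes the 6-month imaging mandatory but gives no outcome if it is missed.

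**What is already known.** SAP 4.6.1: "An interim analysis was performed in January 2017 after inclusion of 46 patients (44 evaluable for the primary endpoint"). It reports 22 responders among the 44, against a requirement of 19.

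**The concern.** The primary result is a single proportion set against a fixed 25%, so the outcome given to each patient without a 6-month scan goes straight into the estimate. Two situations are left open.

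1. **Living, evaluable, last imaged before 6 months.** No rule in 5.1.2 applies. The general conventions then take over, and read literally they leave out of the percentage a patient whom 5.1.2 puts in the population. The numerator stays the same and the denominator shrinks, so the rate is higher than if the patient were counted as a non-responder.
2. **Response documented only after 6 months.** The matching late non-responder is settled by rule. The late responder is settled case by case, with no stated criterion and no outcome if the review cannot decide. A central reader can read the late scan but cannot read a 6-month scan that was never made. Whether a later response stands for response at 6 months is a matter of definition, and the SAP should supply it.

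The timing adds weight. The SAP already contains the interim result and the final analysis is still to come (SAP 4.6.2), so any open classification would be settled with 22/44 known.

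**Working it through.** **Step 1. The plan's own figures.** Inputs from protocol XII.3: p0 = 25%, p1 = 40%, 43 + 43 patients, stage 1 limits 10 and 18, final limit 29. Exact binomial enumeration gives a type I error of 4.74% and power of 90.2%, in line with the stated 5% and 90%. The Fleming stage 1 efficacy limit is n1·p0 + 1.645·√(N·p0·(1 − p0)), rounded to the nearest integer, plus 1:
- n1 = 43, N = 86: 10.75 + 1.645 × 4.016 = 17.36, giving 18, as stated.
- n1 = 44, N = 87: 11 + 1.645 × 4.039 = 17.64, giving 19, as stated in SAP 4.6.1. N = 86 or 88 also gives 19.

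The design and the adapted interim limit therefore reproduce. The problem is a missing rule, not a wrong number.

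**Step 2. Each kind of evaluable patient without a 6-month scan, against the text.**

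| Situation | Outcome under SAP 5.1.2 |
|---|---|
| Died within 6 months | Failure |
| Alive, later scan, no response | Non-responder |
| Alive, later scan, response | Review; no criterion or default |
| Alive, last scan before 6 months | None |

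The last row falls to SAP 6.4 and 6.6. SAP 6.4 makes an exception only for specified cases, and this one is not specified.

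**Step 3. Effect of one patient of each kind.** The documents give no counts, so these are assumed cases on the interim figures. Lower limits are one-sided 95% exact (Clopper-Pearson), the interval that SAP 7.3.2 plans.

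| Case | Rate | Lower limit |
|---|---|---|
| As reported | 22/44 = 50.0% | 36.8% |
| One patient with early imaging only, dropped under SAP 6.6 | 22/43 = 51.2% | 37.7% |
| One late-only responder among the 22, counted as non-response | 21/44 = 47.7% | 34.6% |

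The shifts are +1.2 and −2.3 percentage points. The first is upward relative to counting non-response. If the dropped patient had truly been in response at 6 months, the full count would be 23/44 = 52.3% and dropping would understate it. The true direction for any one patient is therefore unknown.

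**Step 4. Distance to a different decision.** Moving m of the 22 responders to non-response, with 44 kept as denominator:

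| m | Rate | Lower limit | Meets 19/44 |
|---|---|---|---|
| 3 | 19/44 = 43.2% | 30.4% | Yes |
| 4 | 18/44 = 40.9% | 28.4% | No |
| 5 | 17/44 = 38.6% | 26.3% | No |
| 6 | 16/44 = 36.4% | 24.3% | No |

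Four reclassified responders are needed to miss the interim limit, and six before the lower limit falls below 25%.

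**The case against.** **The specific rule should prevail over the general one.** SAP 5.1.2 defines the population as all evaluable patients, and SAP 7.3 assigns that population to the primary endpoint. SAP 6.6 is a general convention for describing variables. The one applied example, the interim, used all 44 evaluable patients as denominator. This has force: nothing shows that anyone was dropped. But it only protects the denominator. It does not say what outcome the patient receives, and the only written text on missing values still points to omission.

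**A reader might infer that nobody is responsible for the review.** The documents do not support that. The endpoint rests on centralized review and protocol X names an independent panel, so central review is the evident route. What is missing is the criterion and the default. SAP 7.3.1 also admits the investigator's opinion where review is not possible, in an open-label trial.

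**Such patients should be rare.** The 6-month scan is mandatory, and the late non-responder rule is conservative. Both points stand and limit the size. However, the SAP itself provides for patients without that scan, so it expects some. Nor can the 5% allowance for loss or non-evaluability be used to guess how many: it covers the step from included to evaluable patients, which at the interim was already the step from 46 to 44.

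**No consequence is shown.** This is correct, and it sets the severity.

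**Conclusion.** The concern holds as two missing outcome rules for the primary endpoint, at minor severity. One group has no assigned 6-month outcome, and the stated defaults, read literally, would take it out of the denominator. The other goes to a review with no criterion, after the interim result is known. One patient of either kind moves the reported rate by about 1 to 2 points, on the assumption that such a patient exists among the 44.

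A reader might go further and infer that the reported 50% is inflated, or that the stop for efficacy is unsafe. The documents support neither. No patient is shown to belong to either group, the interim denominator was the full evaluable set, and the margin over the interim limit is three patients. Some patients in either group may truly have been in response at 6 months, so even the direction of any bias is not established.

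**What to change.** In SAP 5.1.2, with a matching sentence in SAP 6.6:

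1. Define a window around 6 months for the primary assessment. Without one, a response on a scan made a few days early would become non-response under item 2.
2. Count patients in the primary-endpoint population with no assessment in or after that window as non-responders, and state that the missing-value convention of SAP 6.6 does not apply to the response endpoints.
3. Fix in advance, under central review, the outcome of late-only responders: for example, non-responder unless an earlier scan shows response with no progression in between.
4. Report how many patients are classified under each rule. If both groups are empty, this closes the question.

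A response rate on all included patients may be added, but it is a separate option: it addresses the exclusion of non-evaluable patients, not these two gaps.

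The cost is a few sentences and a line of counts, with no new data. The reported response rate may fall slightly.

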### **5.1.3 Tolerance population (SP)**

The tolerance population is defined as the intention-to-treat population having received at least one chemoembolization.

Tolerance criteria will be assessed for this population.

A list of patients excluded from the SP population will be provided, together with the reasons for their exclusion.

## **5.2 Definition of analysis subgroups**

Not applicable.

# **6 General information on statistical methods**

Statistical analyses will be carried out by CRGA.

## **6.1 Software**

Statistical analyses will be carried out using SAS software version 9.4 or later. Some graphs may be produced using R software version 2.11 or later.  
data.

## **6.2 Agreements concerning dates and durations**

Time since inclusion will be defined as the time elapsed since the day of inclusion, the day of inclusion being considered as day 1.

Time since start of treatment will be defined as the time elapsed since the day of the first treatment course, the day of the first treatment course being considered as day 1.

As a result, durations are calculated using the following rule, for example for the time elapsed between death and inclusion: day of death - day of inclusion **+ 1**.

The day preceding the day of inclusion (*resp.* the day preceding the day of treatment) will be considered as day -1 (day 0 does not exist).

The date of last news will default to the date of the last examination/monitoring performed.

The following conversion rules will be used to convert numbers of days into numbers of months or years:  
1 month = 30.4375 days; 1 year = 365.25 days.

## **6.3 Outlier conventions**

Outliers will be confirmed by the investigating center. In the event of confirmation, their value will not be modified, and will be taken into account as it is during the analysis.

## **6.4 Missing data conventions**

Except in the cases specified, missing data will not be replaced.

## 6.5 Baseline definition

Baseline measurements are the last measurements taken at inclusion. In the event of missing data, the last measurement taken before the first treatment is used.

## 6.6 Statistics

**Quantitative variables** will be described using headcount, median, mean, standard deviation of the mean, minimum, maximum and inter-quartile range (Q1-Q3). Quantitative variables can be categorized using their median or a cut-off known from the medical literature.

**Categorical variables** will be described using percentages, and if necessary their bilateral 95% confidence intervals (calculated using the exact method).

Missing values are not taken into account when calculating frequencies and percentages.

The **confidence intervals** provided will be two-sided 95% confidence intervals, except for the main criterion where a one-sided 95% confidence interval will be given.

**Survival data** will be estimated and plotted using the Kaplan-Meier method (Kaplan and Meier, 1958). This will be described by the median and rates calculated at different times. 95% confidence intervals will be provided. Confidence intervals for rates will be constructed from the Greenwood variance calculated using the log-log transformation.

The median follow-up time is calculated using the reverse Kaplan-Meier method (Shemper, 1996).

The treatment hazard ratio will be estimated using a univariate Cox model (Cox, 1984). The hypothesis of proportionality of rates will be tested using the graphical representation and test based on Schöenfeld residuals (Grambsch, 1994); the linearity of the effect of continuous variables on risk will be assessed using the graphical representation of martingale residuals. Confidence intervals for Cox model coefficient estimates will be calculated using Wald's method.

# 7 Statistical analysis

## 7.1 Patient characteristics at inclusion

### 7.1.1 Patient eligibility

#### Population ITT

Patients' eligibility for inclusion will be verified and described by :

- Number and percentage of patients who met all inclusion criteria
- Number and percentage of patients who met all non-inclusion criteria
- Number and percentage of patients who met all criteria (inclusion and non-inclusion)

### 7.1.2 Demographic characteristics

#### Population ITT

The following characteristics at inclusion will be described:

- Inclusion center (number of patients included per center)
- Age (year)
- Gender (Male vs Female)

### 7.1.3 Clinical features

#### Population ITT

The following characteristics at inclusion will be described:

- WHO general status (0 vs 1)
- BMI (kg/m^2)
- BCLC (A vs B vs C)
- Child-Pugh (A vs B7 vs B8 vs B9 vs no cirrhosis)
- Pain assessment
- Medical history :
  - Etiology of hepatopathy (hepatitis B, hepatitis C, alcohol, hemochromatosis, metabolic disease, other)
  - Presence of associated cirrhosis (Yes vs. No)
  - Presence of metabolic syndrome (Yes vs. No)

